Prediabetes is a condition with intermediate hyperglycemia, and based on the American Diabetes Association criteria(22) can be defined as: i) impaired fasting glucose (IFG): FPG ≥ 5.5 mmol/L [≥ 100 mg/dl]; ii) impaired glucose tolerance (IGT): 2 h plasma glucose ≥ 7.8 mmol/L [140 - 199mg/dl]; and iii) IFG + IGT: FPG ≥ 5.5 mmol/L [≥ 100 mg/dl] and 2 h plasma glucose ≥ 7.8 mmol/L [140 - 199mg/dl]. Most of the physiopathological abnormalities observed in T2D, have been already reported in prediabetes with a different severity (23), IR (24), pancreatic β -cell dysfunction (10, 11, 25, 26), pancreatic α -cells dysfunction and relative hyperglucagonemia (13, 15, 25), incretin defect, although it has been questioned whether incretin defect is a cause(27) or consequence of hyperglycemia in T2D (28). It has been previously shown that clinical and physiopathological characteristics are different between these three categories of prediabetes. IFG mainly presents hepatic insulin resistance and mild

impairment on first phase insulin secretion (β -cell dysfunction), IGT is more related to muscle insulin resistance and first and second phase insulin secretion (β -cell dysfunction), while the combination of IFG+IGT present marked pancreatic β -cell dysfunction and whole body IR, with the greatest risk to develop T2D.

Prevalence of prediabetes varies between 9.7 to 56.8 %; in Mexico it has been reported to be around 30 % (29). Eventually, most of the patients with prediabetes (70-80 %) will develop T2D during their life, and of note, they have a higher risk and may already present micro and macrovascular complications (30).

Pancreatic β -cell function has been reported as one of the main factors involved in the progression from prediabetes to T2D in observational studies as well as in clinical trials (31-33)

Different pharmacologic and non-pharmacologic strategies have been used to reduce the progression risk from prediabetes to diabetes and prevent T2D. Lifestyle modification programs, based on physical activity and nutrition, have proved to be a useful strategy, reducing the risk up to 58 % in patients with IGT, in China and Finland (34) (35). The Diabetes Prevention Program Study (DPP) was designed to compare the risk reduction between an intensive lifestyle program vs placebo and metformin (36); DPP by the first time evaluated the effect of metformin, an insulin sensitizer that mainly reduces hepatic glucose production(37); this study showed also a risk reduction of 58 % in the lifestyle group, and only 31 % in the metformin group, in comparison to the placebo group; however, the main limitation of the lifestyle programs is the adherence to the program, and that besides of that, there is a progression from prediabetes to T2D and eventually most of the patients will develop T2D in the long term follow-up, since in the DPP Outcome Study(38) the cumulative T2D incidence at 15 years of follow-up was 55, 56 and 62 % in the lifestyle, metformin and placebo group, respectively.

Other kind of drugs have been also used to prevent T2D; rosiglitazone in the DREAM study showed a 62 % risk reduction in patients with IGT to develop T2D (39), in the ACT-NOW Study, Pioglitazone showed a 72 % risk reduction in patients with IGT, but was associated with significant weight gain and edema, perhaps due to the used dose(40).

Few studies have been performed to evaluate the effect of incretin drugs to prevent T2D. If there is a reduction in the incretin effect in prediabetes, there is two ways of improving it, with GLP-1 receptor agonist or GLP-1 analogues, or with the use of a DPP-IV inhibitor, that eventually will increase endogenous GLP-1 levels two or three-fold. Most of the previous studies have been done with GLP-1 RA or agonist. Exenatide, a GLP-1 receptor agonist, after 24-weeks, in patients with obesity and prediabetes, together with a lifestyle program showed reductions in calorie intake and glucose normalization, but without a difference in fasting, 2h glucose and T2D incidence, but with a mean body weight reduction of around 4.0 kg(41). Liraglutide 1.8 mg/d, also in patients with prediabetes or early T2D (<12 months), was compared to a lifestyle modification program in a small sample of patients (n=40), achieving in both groups a weight reduction of around 7.0 kg, and a slightly better improvement in 2h glucose and β -cell function in the liraglutide group(42); also in patients with prediabetes, liraglutide showed to improve glucose values during OGTT and β -cell function during 14 weeks of treatment(43). At doses of 3.0 mg/d, liraglutide together with diet and exercise has shown a reduction in the incidence of T2D (HR 0.21 95% CI 0.13-0.34, p <0.0001), and improvement in glucose during OGTT in patients with overweight-obesity and prediabetes during a 3 year study (44).

Endogenous GLP-1 is inactivated in 1-4 minutes by the DPP-IV, and with DPP-IV inhibitors the incretin effect gets improved; the use of DPP-IV inhibitors in prediabetes has been less explored, since there are few studies with short duration and small sample size; in an 8-week study, sitagliptin showed no effect in patients with IFG(45), but in patients with IGT it was reported a reduction in glucose levels as well as an improvement in insulin and glucagon levels during OGTT(46). In a 12-week study in patients with overweight and prediabetes, sitagliptin improved also glucose profile and β -cell function during OGTT (47). Saxagliptin in a 24-week study (n = 5-7 per group), showed similar changes than metformin in fasting glucose and HbA1c and a slightly better improvement in 2 h glucose levels in patients with IFG or IGT(48). Linagliptin has been used only in 12-week study (n=8 per group) in comparison to metformin in overweight-obese patients with IGT, finding mainly a reduction in 2h glucose with linagliptin (49).

Linagliptin is a potent and selective DPP-IV inhibitor with a long half-life to be used once daily; it is the only DPP-IV inhibitor cleared mainly by the liver (>80 %) and by consequence it can be used without dose adjustment in patients with high risk or any kind of renal dysfunction (50); besides this, linagliptin has shown in recent clinical trials a safe profile regarding renal and cardiovascular function (51), and has proven efficacy in T2D treatment as a monotherapy or combined therapy (52)

In human islets from non-diabetic and diabetic donors, linagliptine has shown to better improve insulin secretion, β -cell function and α -cell function in non-diabetic islets, suggesting that this kind of drugs could have a better effect at very early stages of the disease, like prediabetes (53).

Few studies have tried to evaluate integral and realistic interventions to prevent T2D, focusing these therapies to the group of patients with prediabetes at the highest risk to develop T2D, combining oral and practical medications with a realistic and real life feasible lifestyle program, and moreover, no study has deeply evaluated the physiopathological effects of such therapies.

The goal of this work was to evaluate the effect of linagliptin + metformin to improve glucose metabolism and pancreatic β -cell function in patients with prediabetes who do not achieve normoglycemia after 12 months of treatment with metformin alone.

Methods

Study design and participants

The RESCATHHEME project (Rescue After Therapy with Metformin for Diabetes Prevention) is a single center double-blind randomized clinical trial performed in patients with IGT. Patients will be selected from a metabolic cohort study performed at the Metabolic Research Laboratory in the University of Guanajuato, México, as part of the University Cohort Project CARE-In-DEEP Study (Cardiometabolic Risk Evaluation and Interdisciplinary Diabetes Education and Early Prevention). For this particular study, patients will be screened with anthropometrical, physical activity, nutritional, biochemical and metabolic evaluation, including oral glucose tolerance test. Patients are eligible for enrollment in the study according

to the following criteria: *i*) persistence of impaired glucose tolerance (2 h glucose 140-199mg/dl [7.8 to 11.0 mmol per liter]) during a single oral glucose tolerance test after 12 months of treatment with 1700mg/day of metformin, and *ii*) age between 18 – 65 years; exclusion criteria: *i*) treatment with drugs affecting glucose levels during the previous 3 months, *ii*) previous pathological conditions affecting glucose metabolism or body weight (thyroid disease, Cushing's syndrome, Acromegaly); *iii*) excessive alcohol intake (acute or chronic), *iv*) fasting plasma triglyceride >400mg/dl, *v*) pregnancy, *vi*) Systolic blood pressure >180mmHg or diastolic blood pressure >105mmHg (subjects could be re-screened after hypertension treatment). Written informed consent will be obtained from all participants and the study was approved by the Ethical Council at the Hospital Regional de Alta Especialidad del Bajío (CEI-35-16).

Procedures

Anthropometrical and body composition measurements. Weight will be measured while participants are barefoot and wearing minimal clothing. Height is obtained while the participants are standing barefoot with their shoulders in a normal position. BMI (kg/m²) is obtained from standardized measurements of weight and height and is computed as a ratio of weight (kg):height squared (m²). Waist circumference will be measured at the high point of the iliac crest at the end of normal expiration to the nearest 0.1 cm. Body composition will be assessed with electrical bioimpedance through a Tanita Scale SC-240. All measurements will be performed by personal trained to use standardized procedures and reproducibility is evaluated, resulting in concordance coefficients between 0.88 and 0.94. Weight will be recorded at least every two months, while electrical bioimpedance at basal and at EOS.

Nutritional and Physical Activity Evaluation. A semi-quantitative food frequency questionnaire (FFQ) previously validated (54), will be applied to evaluate dietary intake. This questionnaire included data regarding the consumption of 116 food items. For each food, a commonly used portion size (e.g. 1 slice of bread or 1 cup of coffee) is specified on the FFQ and participants reported their frequency of consumption of each specific food over the previous year. Participants chose from 10 possible responses, ranging from “never” to “6 or more times per day.” For our analysis, the reported frequency for each food item is converted

into a daily intake. Total energy intake is computed by summing the energy intakes from all foods. The PA level of participants is assessed using a self-administered questionnaire that is verified when the patient assist for the metabolic evaluation. The questionnaire has a validated Spanish translation which has been adapted for use in the Mexican population (55). The questionnaire is self-administered and estimates the minutes devoted to the practice of different recreational physical activities during a typical week in the last year (including walking, running, cycling, aerobics, dancing, and swimming as well as playing football, volleyball, basketball, tennis, fronton, baseball, softball, and squash, among other activities). Each item includes time intervals that allow participants to detail the exact number of minutes or hours they dedicate to each form of recreational PA, as well as the intensity of each PA (light, moderate, vigorous). The total duration of each recreational PA is expressed in minutes per day. We calculated the number of hours per week devoted to each activity, which were then multiplied by the intensity of each activity, defined as multiples of the metabolic equivalent (MET) of sitting quietly. We used the Compendium of Physical Activities to assign METs to each activity (56). We then add the average weekly energy expenditure attributable to each activity to derive the total MET-hours per week. Energy intake and physical activity will be evaluated at basal and at the end of the study.

Metabolic evaluation.

Oral glucose tolerance test (OGTT): All subjects will be admitted to the Metabolic Research Laboratory of the Department of Medicine and Nutrition, Division of Health Sciences at the University of Guanajuato the day of the study between 7 and 8 AM, and a catheter will be placed into an antecubital vein for all blood withdrawal. Subjects will not be allowed to eat or drink anything after 10 PM on the night before, until the study is completed. After the intravenous catheter is placed and the first blood sample is drawn, the patients ingest 75 grams of glucose. Serum samples for glucose and insulin measurement will be drawn at -15, and 0 minutes and every 30 minutes thereafter for two hours. Prediabetes is diagnosed based on the OGTT; and only patients with IGT (2 h glucose 140-199 mg/dl), and ideally together, although not exclusively, with IFG (FG 100-125mg/dl) will be included in this study. Patients with newly diagnosed T2D will be excluded from the study.

Measurements. Glucose will be measured with an Analox glucoanalyzer GM9 (Analox Instruments) and by colorimetric glucose oxidase (Vitros 5600; Ortho Clinical Diagnostics). Lipid levels are measured by dry chemistry with colorimetric method (Vitros 5600; Ortho Clinical Diagnostics). Insulin will be measured by chemiluminiscent immunometric assay (IMMULITE 2000 Immunoassay system, Siemens), and Glucagon by Quantikine ELISA Immunoassay (R&D Systems Inc, Minneapolis, USA) with an intra-assay CV of 2.7 – 3.6 %. HbA1c will be determined using high-performance liquid chromatography with a DS-5 Analyzer (Drew Scientific, Inc. Miami, FL, USA).

Calculations. The incremental and the AUC for glucose and insulin during the OGTT are calculated according to the trapezoidal rule. Insulin secretion is calculated dividing the $AUC_{insulin}_{0-120}$ by the $AUC_{glucose}_{0-120}$ during the OGTT. The insulin secretion/insulin resistance (IS/IR) index (disposition index = DI) during OGTT is calculated as $(AUC_{insulin}_{0-120} / AUC_{glucose}_{0-120}) * \text{Matsuda index}$ (57). Insulin sensitivity during OGTT is calculated from the Matsuda index (58), and at fasting with the homeostasis model assessment (HOMA-IR). From the hyperglycemic clamp the incremental and AUC for glucose, insulin and C-peptide are also calculated according to the trapezoidal rule. Different measurements of pancreatic β -cell function will be derived from the hyperglycemic clamp: DI will be obtained as a product of insulin sensitivity (Matsuda index) and the incremental AUC for insulin and C-peptide from 0 to 15 and from 0 to 120 minutes.

Randomization and masking. Patients will be randomly assigned in a 1:1 ratio to receive linagliptin/metformin 2.5/850mg every 12 h + lifestyle modification program, or metformin 850mg every 12 h + lifestyle modification program during 6 months. Randomization will be performed using an electronic random numbers table by a Nutritionist not involved in the study. Participants and investigators involved in the patients follow-up and outcome measurements will be masked to treatment allocation during the entire study.

Interventions. i) Linagliptin + metformin + lifestyle: Patients allocated to this group will start linagliptin/metformin pills of 2.5/850mg once daily during the first month, and after that the dose will be increased to 2.5/850mg twice daily from the second month until the end of the

study (24 months). ii) Metformin + lifestyle: Patients on this group will continue metformin pills of 850mg once daily during the first month, and increased to 850mg twice daily thereafter until the end of the study (6 months). Both groups will receive the same lifestyle implementation program based on a prescribed diet every two months seeking to reduce their body weight at least by 5-7 %, adjusting their energy requirements based on their weight every two months, and composed from 55-60 % of carbohydrates, 25-30 % fat, and 10-15 % proteins. If the patient is sedentary, he or she will be advised to start with 45 min/week of mild to moderate exercise with a specific activity according to patients preference; patients will be counseled to increase the duration and frequency or intensity of exercise every two weeks until reaching 150min/week of moderate activity or 75 min/week of intense activity. If the patient was already physically active, it will be recommended to continue like this and vary its exercise routines.

Follow-up visits and outcome. Patients will have a follow-up visit every month. Every appointment is about 30-45 minutes; medications tolerance and side effects will be recorded in every patients' visit. Nutritional and physical activity assessment according to the patient's weight will be performed by a Nutritionist every month. Monthly adherence to medications will be evaluated by pill counting; nutritional adherence and energy intake will be evaluated at 6 months by a food frequency questionnaire, and physical activity at 0 and 6 months. At basal and at 6 months patients will have an OGTT. Primary objective is to evaluate at 6 months glucose profile during OGTT, insulin secretion and pancreatic β -cell function by the OGTT DI, and regression to normoglycemia; T2D will be diagnosed and confirmed by at least two consecutive measurements of the same criteria: glycated haemoglobin ≥ 6.5 %, fasting glucose ≥ 126 mg/dl, or 2 h glucose ≥ 200 mg/dl.

Statistical analysis

The sample size calculation was based on the fact that we expected an improvement of at least 60 % on the pancreatic β -cell function and glucose profile during the OGTT in patients with the combined treatment and at least an improvement of 20% on the metformin group, based on previous reports about glucose levels and pancreatic β -cell function in prediabetic patients before and after treatment (40, 59); in order to be able to detect a minimum difference of 40 %

between groups in the quantitative measurement of pancreatic β -cell function, and assuming an alpha error of 5% and a beta error of 20%, we require approximately 14 patients per group. The primary analysis is the comparison of the change in glucose profile during OGTT as well as measurements of pancreatic β -cell function during OGTT. Intergroup comparisons between absolute values and delta values will be performed with a t test for independent groups; intra-group comparisons will be performed using a paired t-test. Non-numerical variables will be compared between groups with the chi squared test.

Statistical analyses and graphics will be performed using SPSS Version 21.0 (SPSS Inc) and GraphPad Prism 5.0. Statistical significance is considered when p value is less than 0.05.

REFERENCES

3. DeFronzo RA. Pathogenesis of type 2 diabetes mellitus. *Med Clin North Am.* 2004 Jul;88(4):787-835, ix.
4. Ferrannini E. Insulin resistance versus beta-cell dysfunction in the pathogenesis of type 2 diabetes. *Curr Diab Rep.* 2009 Jun;9(3):188-9.
6. [name], Davalli AM, Chavez AO, Hubbard GB, Dick EJ, Majluf-Cruz A, et al. Pancreatic islet amyloidosis, beta-cell apoptosis, and alpha-cell proliferation are determinants of islet remodeling in type-2 diabetic baboons. *Proc Natl Acad Sci U S A.* 2009 Aug 18;106(33):13992-7.

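### The randomisation section states no blocking or stratification, so it guarantees neither about 14 patients per group nor balance on IFG status; IFG-stratified small blocks and an IFG term are a cheap improvement

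*Combined protocol and SAP*

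**What the plan says.** The Randomization and masking section sets a 1:1 ratio and describes the method in one sentence: "Randomization will be performed using an electronic random numbers table by a Nutritionist not involved in the study". Neither it nor any other section mentions blocks, strata, minimisation or a list fixed at equal numbers.

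Three other places bear on this:

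- **Size.** Statistical analysis says "we require approximately 14 patients per group", so about 28 in all.
- **Population.** The oral glucose tolerance test (OGTT) section admits patients with impaired glucose tolerance (IGT), "ideally together, although not exclusively, with IFG". Patients with and without IFG can therefore both enter.
- **Severity.** The introduction separates the prediabetes categories: "while the combination of IFG+IGT present marked pancreatic" beta-cell dysfunction, and this combined category is given the highest risk of progressing to diabetes.

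The OGTT disposition index, a beta-cell measure, is among the primary objectives. Statistical analysis compares the arms on absolute and change values with an independent-groups t test, without covariates.

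**The concern.** In a trial of about 28 patients, an unrestricted list can leave the arms unequal in size and unequal in the share of patients with the severity marker that the protocol itself names. Nothing in the stated analysis would absorb the second imbalance. At stake is how credible and how precise the between-arm comparison of beta-cell function is. A visible IFG difference between two groups of about 14 would invite the question whether the result reflects treatment or case mix, and an unadjusted t test could not answer it.

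**Working it through.** **Inputs from the protocol.** About 14 per group; 1:1 allocation; "assuming an alpha error of 5% and a beta error of 20" percent; "in order to be able to detect a minimum difference of 40" percent; IGT with or without IFG; unadjusted t test.

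**Assumptions.** An unrestricted list; a two-sided test; exactly 28 patients; 9, 14 or 19 of the 28 with IFG (about one third, one half, two thirds). The protocol gives neither the IFG share nor a standard deviation (SD).

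**1. The plan's own figure.** Fourteen per group cannot be reproduced without an SD. Solving backwards with the noncentral t distribution, 80% power at 14/14 needs a standardised difference d = 1.10, that is an SD of 40/1.10 = 36.4 points. The steps below use d = 1.10.

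**2. Arm sizes.** With X ~ Binomial(28, 0.5), P(14/14) = C(28,14)/2^28 = 14.9%. Power comes from the noncentral t with 26 degrees of freedom and noncentrality d/√(1/n1 + 1/n2).

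| Split | This split or worse | Power at this split |
|---|---|---|
| 14/14 | – | 80.0% |
| 12/16 | 57.2% | 79.2% |
| 11/17 | 34.5% | 78.1% |
| 10/18 | 18.5% | 76.6% |
| 9/19 | 8.7% | 74.4% |

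Weighting power by the probability of each split gives 78.5%, an average loss of about 1.5 points.

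**3. IFG balance.** With m of 28 patients having IFG, the IFG patients in arm 1 are a ~ Binomial(m, 0.5) and the others b ~ Binomial(28 − m, 0.5). The gap is |a/(a+b) − (m−a)/(28−a−b)|. Summing exactly over all allocations:

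| Patients with IFG | Gap of 20 points or more | Gap of 30 points or more |
|---|---|---|
| 9 or 19 of 28 | 28.6% | 11.2% |
| 14 of 28 | 34.6% | 11.0% |

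If the number with IFG is itself random, at shares of 30%, 50% and 70%, simulation gives 26%, 32% and 26% for a gap of 20 points or more.

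**4. What a gap does to the result.** Suppose IFG shifts the outcome by 0.5 to 1.0 SD (assumed). A 20-point gap moves the between-arm difference by 0.20 × 0.5 = 0.10 SD up to 0.20 × 1.0 = 0.20 SD. That is 9% to 18% of the planned 1.10 SD. The standard error at 14/14 is √(2/14) = 0.38 SD.

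**5. The proposed scheme.** I simulated permuted blocks of randomly varied size 2 and 4, separately by IFG status.

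- No allocation had an IFG gap of 20 points; the largest was 14 points.
- Arm sizes differed by at most 2 patients in over 99% of runs and never by more than 4.
- Exactly 14/14 occurred in about 50% of runs with 9 or 19 IFG patients and 79% with 14, or about 65% when the IFG count is random.
- Varied blocks without strata gave 14/14 in about 90%. Unstratified blocks of 4 left an IFG gap of 20 points or more in 30% to 34% of runs, so blocking alone does not address IFG.

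**6. Power with the IFG term.** Total SD is held fixed, so d stays at 1.10 before adjustment. Figures are simulated with 9 or 14 IFG patients.

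| IFG effect (assumed) | Unrestricted, t test | Unrestricted, IFG term | Stratified, IFG term |
|---|---|---|---|
| none | 78% | 77% | 80% |
| 0.5 SD | 79% | 79% | 81–82% |
| 1.0 SD | 78–80% | 86–88% | 89–90% |

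The strata add about 2 to 3 points. Any larger gain comes from the model term and depends on how strongly IFG predicts the outcome.

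**The case against.** **The protocol never says the list is simple.** This stands. Random numbers can also generate a blocked or fixed 14/14 list. A reader might infer that the sponsor chose unrestricted allocation and that the trial will miss its group sizes; the text supports only that no restriction is stated, so neither property is guaranteed.

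**Unequal arms barely matter.** This also stands. A loss of 1.5 power points is small against a target that is itself approximate and rests on an unstated SD. Arm size alone would not justify a change.

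**Chance imbalance is not bias.** Correct: the t test keeps its 5% error rate over repeated randomisation. Analysing change removes additive baseline differences, and the introduction describes severity, not a different response to treatment. It also attributes beta-cell dysfunction to IGT, which every participant has. So the IFG effect on the change in disposition index is unknown and may be small. Against this, absolute values are also to be compared, and those do not subtract baseline. Step 6 shows that stratifying with the term does not lose power against the stated plan even if IFG has no effect.

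**Uneven splits also upset the chi-squared test.** A reader might add this as support. It gives none. The test's maximum exact size is 5.2% at 14/14, 6.4% at 13/15, 5.7% at 12/16, 6.3% at 11/17 and 5.3% at 10/18, with no steady pattern. Stratified blocks with a random IFG count produce 13/15 in about 35% of trials, against 28% for an unrestricted list.

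**The remedy is neither complete nor free.** Agreed: exact equality is not guaranteed, small blocks add some predictability, and the IFG term changes the planned analysis.

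**Conclusion.** The point holds as a cheap improvement, not as an error that invalidates the trial. The stated method does not guarantee about 14 per group or balance on IFG status. If the list is unrestricted, arm-size imbalance costs about 1.5 power points on average. A gap of 20 points or more in IFG share would arise in about 29% to 35% of allocations, and the planned t test would not adjust for it.

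These figures rest on exactly 28 patients, an unrestricted list, an assumed IFG share of one third to two thirds and, for power, a back-solved d of 1.10. The consequence of an IFG gap depends on an IFG effect that the protocol does not give. At an assumed 0.5 to 1.0 SD, stratification with the model term gives power of roughly 81% to 90%, against about 78% to 80% for an unrestricted list with the t test.

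**What to change.** State the restriction explicitly. The same uninvolved person generates a concealed list in permuted blocks of randomly varied size (2 and 4), separately for patients with and without IFG at the qualifying OGTT. In Statistical analysis, replace the primary between-arm t test with a linear model containing treatment and IFG status, preferably with the baseline value of the outcome as well. If a restricted list was already intended, say which.

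The cost is a short time to generate the list, a sentence in the randomisation section and one or two model terms; IFG status is already known from the qualifying test. The downside is that the last allocation in a block is slightly easier to predict. Varied, undisclosed block sizes and the planned masking limit this. If allocation has already begun, the model terms can still be added, provided this is done before unblinding.

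### The primary objective holds three or four outcomes, the primary analysis leaves one of them out, and no rule says what counts as success

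*Combined protocol and SAP*

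**What the plan says.** The Follow-up visits and outcome section reads "Primary objective is to evaluate at 6 months glucose profile during OGTT, insulin secretion and pancreatic" β-"cell function by the OGTT DI, and regression to normoglycemia". This can be read as four outcomes (glucose profile, insulin secretion, DI, normoglycemia), or as three if insulin secretion and β-cell function are both judged by DI. The Calculations section gives insulin secretion its own formula (insulin AUC over glucose AUC) and defines DI as that ratio times the Matsuda index, which favours four.

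The Statistical analysis section says "The primary analysis is the comparison of the change in glucose profile during OGTT as well as measurements of pancreatic" β-cell function during the OGTT. The plural can cover both insulin secretion and DI, but they are not listed. Normoglycemia is not named there; it is covered only by the general sentence "Non-numerical variables will be compared between groups with the chi squared test". Numerical outcomes get two-sample t tests on both absolute values and changes. The only decision rule is "Statistical significance is considered when p value is less than 0.05".

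The sample size is set to detect a 40% difference "between groups in the quantitative measurement of pancreatic" β-cell function: "assuming an alpha error of 5% and a beta error of 20%, we require approximately 14 patients per group". The index is not named, and the expected improvement behind it covers β-"cell function and glucose profile during the OGTT in patients with the combined treatment".

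**The concern.** Two sections define the primary question differently, and neither says when it has been answered. Nothing states whether one significant outcome is enough or whether all are needed, and the two rules have opposite consequences.

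- **Any one suffices.** Each extra test adds a chance of a false positive, so the 5% alpha used to size the trial no longer describes the claim that the primary objective was met.
- **All are required.** Alpha is protected, but 14 per group no longer gives 80% power.

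Glucose profile also has no single summary, because the Calculations section derives both total and incremental AUC. With about 28 patients in all, one nominal p<0.05 among several candidates could be reported as primary success, and a reader could not tell whether that was the intended rule.

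**Working it through.** **1. The plan's own figure.** Inputs from the Statistical analysis section are a difference of 40 percentage points, alpha 5%, power 80% and 14 per group. No SD is given and sidedness is not stated, so 14 cannot be reproduced directly. Taking a two-sided test and solving backwards from n = 2(1.96 + 0.84)²(SD/40)² = 14 gives SD ≈ 37.8 points. The exact t-test calculation gives SD ≈ 36.4, so the standardized effect is d = 40/36.4 ≈ 1.10. Noncentral t power at d = 1.10 and n = 14 is 80.0%.

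**2. Any one suffices, independent tests at exact 5% size.** The chance of at least one p<0.05 under no effect is 1 − 0.95^k:
- k = 2: 9.75%
- k = 3: 14.3%
- k = 4: 18.5%

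**3. Any one suffices, correlated outcomes.** The outcomes share components, so they are correlated, but the documents give no values. Assumptions: 14 per group, equicorrelated outcomes (correlation r), baseline-to-follow-up correlation 0.5, and two-sample t tests on change. Normoglycemia is follow-up glucose below a cut-off that 20%, 30% or 50% of patients meet. There were 60,000 simulated null trials per scenario. Ranges in the table run over the three normoglycemia rates.

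| Tests counted | r = 0 | r = 0.5 | r = 0.7 | r = 0.9 |
|---|---|---|---|---|
| Two changes (glucose profile, DI) | 10.0% | 9.0% | 8.2% | 7.1% |
| Three changes (plus insulin secretion) | 14.2% | 12.4% | 11.1% | 8.4% |
| Two changes + normoglycemia, uncorrected chi-squared | 13.4–14.4% | 12.2–13.3% | 11.5–12.5% | 10.4–11.4% |
| Same, continuity-corrected | 11.4–11.7% | 10.4–10.8% | 9.5–10.0% | 8.3–8.8% |
| Three changes + normoglycemia, uncorrected | 17.3–18.2% | 15.6–16.6% | 14.3–15.1% | 11.8–12.8% |
| Same, continuity-corrected | 15.4–15.7% | 13.7–14.1% | 12.4–12.7% | 9.7–10.1% |

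The correction matters because counts are small: at 20% normoglycemic the expected count is 0.20 × 14 = 2.8 per arm. Fisher's exact test matches the corrected rows.

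**4. Sensitivity.**
- Baseline-to-follow-up correlation of 0.3 or 0.7 (checked at r = 0.5 and 0.9) moves the figures by less than 1 point.
- Linking normoglycemia to the other outcomes through a correlated latent variable, instead of thresholding glucose, lowers the four-outcome figures at r = 0.9 to 10.5–11.3% uncorrected and 9.2–9.4% corrected.
- Normoglycemia rates of 5–10% give about 8–14.5% for four outcomes.
- The table counts one test per numerical outcome. Testing absolute values as well as changes for just two outcomes gives 13–16% (r = 0.9 to 0.5).

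**5. All required.** With d = 1.10 on every endpoint, 14 per group and each test at 0.05, power at r = 0.5 / 0.7 / 0.9 is:
- both of two endpoints: 68.4 / 70.9 / 74.8%
- all three numerical outcomes: 60.8 / 65.5 / 72.1%

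**The case against.** **The sample size already singles out β-cell function.** The 40% difference is tied to it, so DI could be taken as the real primary. But no index is named in that calculation, the expected improvement also covers glucose profile, and the primary analysis pairs the two again. Sizing on one outcome does not make it the only primary. The argument is a good reason to choose DI, not evidence that the plan has done so.

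**The Statistical analysis section should govern.** The family would then be two or three change tests, and the 12–17% range would not apply. This is fair: that range needs the four-outcome reading, normoglycemia as a primary test, an uncorrected chi-squared test and an any-success rule together. The smaller family still gives 7–9% or 8–13%, and the conflict with the stated objective remains.

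**The two items may be meant jointly.** A both-required reading is equally open and does not inflate alpha. That stands, but the cost then falls on power.

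**The percentages rest on assumptions.** They do. Patients enter with impaired glucose tolerance persisting after a year of metformin, so a normoglycemia rate below 20% is plausible and lowers the upper figures. No scenario examined came down to 5%.

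**Conclusion.** The concern holds. The objective and the primary analysis do not match, and the plan has no single primary endpoint, test order, adjustment or success rule. That follows from the text and depends on no assumed number.

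The size is illustrative. If any one success counts, the false-positive risk is 7–9% for two change tests, 8–13% for three, and 12–17% (uncorrected) or 10–14% (corrected) for four outcomes, given correlations of 0.9 to 0.5 and 20–50% normoglycemic. These are not bounds: weaker correlation raises them, and rarer normoglycemia lowers the four-outcome figures. If two endpoints must both succeed, power is about 68–75%, assuming a two-sided test and the same back-solved effect on each. This should be corrected. It affects what a positive result would mean, not patient safety.

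**What to change.** Before unblinding, put one primary endpoint and one two-sided 0.05 test in the same words in both sections. For example: *The primary endpoint is the between-group difference in change in OGTT DI from baseline to 6 months, compared with a two-sample t test.* DI is the natural choice, since it has a formula in the Calculations section and the sizing rests on β-cell function. State whether change is absolute or relative; the sizing is in percentages, so a relative scale matches it. Make the tests of absolute values secondary.

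Make one glucose summary (for example AUC 0–120), insulin secretion and regression to normoglycemia secondary. Either test them in a fixed order after DI or report them as estimates with 95% confidence intervals.

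This costs only wording, with no extra patients. The downside is that an effect on glucose profile alone could no longer be called a primary success.

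If glucose profile is to stay a second primary, as the Introduction's goal might suggest, fix its summary, choose a rule and restate the power. With d = 1.10 on both endpoints:
- **Alpha split, 0.025 each:** 70.1% power per endpoint at 14 per group; about 17 per group restores 80% (79.9%).
- **Both required at 0.05:** about 68–75% at 14 per group; 18, 17 or 16 per group restores at least 80% at correlations of 0.5, 0.7 and 0.9 (82.1%, 81.1%, 81.2%).

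These figures inherit the two-sided assumption. If the sizing was one-sided, d is about 40/41.4 = 0.97 and they need recalculating.
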